## 5.2 SAFETY ENDPOINTS

Not applicable

[figure not shown]
CCI

PFIZER CONFIDENTIAL

CT24-WI-GL03-RF03 2.0 *Non-Interventional Statistical Analysis Plan For Secondary Data Collection*  
*Study 01-Jun-2020*  
 Page 10 of 30

CCI

PFIZER CONFIDENTIAL

CT24-WI-GL03-RF03 2.0 *Non-Interventional Statistical Analysis Plan For Secondary Data Collection*  
Study 01-Jun-2020  
Page 11 of 30

CCI

## <Derivation of categorical variables>

Item	Derivation method
Age (2 categories )	Age is divided into the following categories: <75 years; $\geq$ 75 years
Age (3 categories )	Age is divided into the following categories: <65 years; $\geq$ 65 years and <75 years; $\geq$ 75 years
Body mass index (BMI) (3 categories )	BMI is divided into the following categories: <25 kg/m  ; $\geq$ 25 kg/m  ; Unknown
C-reactive protein (CRP) (3 categories )	CRP is divided into the following categories: <5 mg/L; $\geq$ 5 mg/L; Unknown ※ Categorized as "Unknown" if CRP is missing (Not measured)
Estimated glomerular filtration rate (eGFR) (3 categories )	eGFR is divided into the following categories: <60; $\geq$ 60; Unknown ※ Categorized as "Unknown" if eGFR is missing (Not measured)
Fuhrman grade (3 categories )	Fuhrman grade is divided into the following categories: Grade 1 or Grade 2; Grade 3 or Grade 4; Unknown

PFIZER CONFIDENTIAL

CT24-WI-GL03-RF03 2.0 *Non-Interventional Statistical Analysis Plan For Secondary Data Collection*  
*Study 01-Jun-2020*  
 Page 12 of 30

Metastatic site: Lung	"Yes" will be selected if the presence or absence of metastasis is "Yes" and the metastatic site is "Lung." "No" will be selected if the presence or absence of metastasis is "Yes" and the metastatic site is not "Lung" or if the presence or absence of metastasis is "No." "Unknown" will be selected if the presence or absence of metastasis is "Unknown."
Metastatic site: Liver	"Yes" will be selected if the presence or absence of metastasis is "Yes" and the metastatic site is "Liver." "No" will be selected if the presence or absence of metastasis is "Yes" and the metastatic site is not "Liver" or if the presence or absence of metastasis is "No." "Unknown" will be selected if the presence or absence of metastasis is "Unknown."
Metastatic site: Bone	"Yes" will be selected if the presence or absence of metastasis is "Yes" and the metastatic site is "Bone." "No" will be selected if the presence or absence of metastasis is "Yes" and the metastatic site is not "Bone" or if the presence or absence of metastasis is "No." "Unknown" will be selected if the presence or absence of metastasis is "Unknown."
Metastatic site: Brain	"Yes" will be selected if the presence or absence of metastasis is "Yes" and the metastatic site is "Brain." "No" will be selected if the presence or absence of metastasis is "Yes" and the metastatic site is not "Brain" or if the presence or absence of metastasis is "No." "Unknown" will be selected if the presence or absence of metastasis is "Unknown."
Metastatic site: Regional lymph node	"Yes" will be selected if the presence or absence of metastasis is "Yes" and the metastatic site is "Regional lymph node." "No" will be selected if the presence or absence of metastasis is "Yes" and the metastatic site is not "Regional lymph node" or if the presence or absence of metastasis is "No."

PFIZER CONFIDENTIAL

CT24-WI-GL03-RF03 2.0 *Non-Interventional Statistical Analysis Plan For Secondary Data Collection*  
*Study 01-Jun-2020*  
 Page 13 of 30

	"Unknown" will be selected if the presence or absence of metastasis is "Unknown."
Metastatic site: Distant lymph node	"Yes" will be selected if the presence or absence of metastasis is "Yes" and the metastatic site is a "Distant lymph node." "No" will be selected if the presence or absence of metastasis is "Yes" and the metastatic site is not a "Distant lymph node" or if the presence or absence of metastasis is "No." "Unknown" will be selected if the presence or absence of metastasis is "Unknown."
Metastatic site: Other	"Yes" will be selected if the presence or absence of metastasis is "Yes" and the metastatic site is "Other." "No" will be selected if the presence or absence of metastasis is "Yes" and the metastatic site is not "Other" or if the presence or absence of metastasis is "No." "Unknown" will be selected if the presence or absence of metastasis is "Unknown."
ECOG Performance Status ①	ECOG Performance Status is divided into the following categories: 0; 1; $\geq 2$
ECOG Performance Status ②	ECOG Performance Status is divided into the following categories: 0 or 1; $\geq 2$
Number of risk factors (7 categories )	The number of risk factors is divided into the following categories: 0; 1; 2; 3; 4; 5; 6
Initial dose of avelumab [daily dose (mg)]	The initial dose of avelumab is divided into the following categories: $<10 \text{ mg/kg}$ ; $10 \text{ mg/kg}$ ; $>10 \text{ mg/kg}$
Initial dose of axitinib [daily dose (mg)]	The initial dose of axitinib is divided into the following categories: $<2 \text{ mg}$ ; $\geq 2 \text{ mg}$ and $<5 \text{ mg}$ ; $\geq 5 \text{ mg}$ and $<10 \text{ mg}$ ; $<10 \text{ mg}$ ; $10 \text{ mg}$ ; $>10 \text{ mg}$
Presence or absence of changes in the avelumab dose	"Yes" will be selected if the dose of avelumab was changed even once. "No" will be selected if the dose was unchanged.
Presence or absence of changes in the avelumab dose (dose reduction)	"Yes" will be selected if the dose of avelumab was changed (dose reduction) even once. "No" will be selected if the dose was unchanged (dose reduction).

PFIZER CONFIDENTIAL

CT24-WI-GL03-RF03 2.0 *Non-Interventional Statistical Analysis Plan For Secondary Data Collection*  
 Study 01-Jun-2020  
 Page 14 of 30

Presence or absence of change in the dose of avelumab (dose increase)	"Yes" will be selected if the dose of avelumab was changed (dose increase) even once. "No" will be selected if the dose was unchanged.
Presence or absence of changes in the axitinib dose	"Yes" will be selected if the dose of axitinib was changed even once. "No" will be selected if the dose was unchanged.
Presence or absence of changes in the axitinib dose (dose reduction)	"Yes" will be selected if the dose of axitinib was changed (dose reduction) even once. "No" will be selected if the dose was unchanged.
Presence or absence of changes in the axitinib dose (dose increase)	"Yes" will be selected if the dose of axitinib was changed (dose increase) even once. "No" will be selected if the dose was unchanged.
Administration of high-dose corticosteroid therapy for iRAE	"Yes" will be selected if the prednisolone-equivalent* daily dose was $\geq 40$ mg. Otherwise, "No" will be selected.

\*In addition, the corticosteroid-equivalent dose (prednisolone-equivalent) is calculated as the dose of the drug  $\times$  prednisolone conversion ratio, according to the table below:

General name	Corresponding dose (mg)	Prednisolone conversion ratio
Cortisone	25	0.2
Hydrocortisone	20	0.25
Prednisolone	5	1
Methylprednisolone	4	1.25
Triamcinolone	4	1.25
Dexamethasone	Approximately 0.75	6.67
Betamethasone	Approximately 0.75	6.67

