## 6 HANDLING OF MISSING VALUES

An absence of data for analysis will be treated as missing values, and no special imputation processing will be performed using statistical methods. In addition, the missing data regarding dates will be treated as follows:

- ✓ If "year" is unknown: Missing
- ✓ If "month" is unknown: July
- ✓ If "day" is unknown: day 15
- ✓ If "month" and "day" are unknown: July 1

Other than the above, the imputation of the missing values will not be performed, unless otherwise specified.

If the above imputation measures result in the reversal of dates when calculating the number of days (e.g., the number of days from the initiation to the end of the treatment), it will not be adopted for analysis.

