##### 【Division of categorical variables】

Factor	Category
Administration of corticosteroid therapy for irAEs	No; Yes; Unknown
Administration of high-dose corticosteroid therapy for irAEs	No; Yes

irAEs, immune-related adverse events

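### The high-dose corticosteroid flag has no Unknown level, so unknown steroid use and unrecorded or unconvertible doses are coded No

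*SAP*

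**What the plan says.** Describing corticosteroid use for irAEs is a secondary objective (protocol 8.2, SAP 2.2). SAP 7.2.2.8 serves it with one continuous variable, the duration of corticosteroid treatment, and two categorical variables: any corticosteroid, and high-dose corticosteroid. It reports these in both the FAS and the efficacy analysis set.

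The high-dose flag is derived in the SAP section 5 table of categorical variables. It is Yes when the prednisolone-equivalent daily dose is at least 40 mg, using a conversion table of seven named steroids. For the rest the rule is "Otherwise, 'No' will be selected".

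The category list in 7.2.2.8 agrees with that rule: "Administration of high-dose corticosteroid therapy for irAEs No; Yes". The row for the parent variable differs: "Administration of corticosteroid therapy for irAEs No; Yes; Unknown".

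SAP section 6 gives the general rule: "An absence of data for analysis will be treated as missing values, and no special imputation processing will be performed using statistical methods". After the rules for partial dates it adds that "the imputation of the missing values will not be performed, unless otherwise specified".

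**The concern.** The plan expects that steroid use will be unknown for some patients, since it gives the parent variable a level for them. It gives the high-dose flag no such level and sends every case that does not meet the Yes condition to No. Three kinds of patient without the needed information then look the same as patients documented to be below the cut-off:

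- those with Unknown steroid use;
- treated patients with no recorded drug or dose;
- treated patients given a steroid outside the seven in the conversion table, whose dose cannot be converted.

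Missing entries are foreseeable. This is a retrospective chart review that collects data where available (protocol 9.2), and protocol 9.9 lists missing data as a limitation. At stake is a high-dose share that may be too low, in one of only two categorical outputs for this objective.

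**Working it through.** The plan states no figure that depends on this rule, and protocol 9.5 says sample size calculations do not apply. The check is therefore to follow the rule case by case and then show how its effect scales.

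**Following the rule**

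| Patient | Parent variable | High-dose flag, read literally |
|---|---|---|
| Documented dose of 40 mg or more | Yes | Yes |
| Documented dose below 40 mg | Yes | No |
| Treated; drug or dose missing or not convertible | Yes | No |
| Documented non-use | No | No |
| Steroid use Unknown | Unknown | No |

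The third and fifth rows are the problem.

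**Comparable variables.** In the same SAP section, each metastatic-site flag carries Unknown through from its parent. CRP and eGFR become Unknown when not measured. BMI and Fuhrman grade have an Unknown level. The practice is not universal: sarcomatoid component and the individual IMDC factors are listed only as Yes and No. Those lists, however, come with no catch-all rule that turns an absent value into No.

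**Conversion table.** The ratios should equal 5 divided by the corresponding dose: 5/25 = 0.2, 5/20 = 0.25, 5/5 = 1, 5/4 = 1.25 (two drugs) and 5/0.75 = 6.67 (two drugs). All seven agree with the SAP, so the issue is the catch-all and not the conversion.

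**Scaling.** Let N be all patients, U those with unknown status, and H those documented as high dose.

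- As coded: H/N
- Among known status: H/(N − U)
- Upper bound, if every unknown were high dose: (H + U)/N

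It follows that H/N = [H/(N − U)] × (1 − U/N). Coding unknowns as No shrinks the known-status share by the unknown fraction. Against the true share, which lies between H/N and (H + U)/N, the coded figure is equal or too low.

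**Illustration.** N = 150 is the expected number in protocol 9.5. The rest is assumed: 0% to 20% unknown, and a high-dose share of 10% to 20% among known patients, with counts rounded.

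| Assumed share among known | U | H | As coded | Among known | Upper bound |
|---|---|---|---|---|---|
| 15% | 0 | 22 | 14.7% | 14.7% | 14.7% |
| 15% | 8 | 21 | 14.0% | 14.8% | 19.3% |
| 15% | 15 | 20 | 13.3% | 14.8% | 23.3% |
| 15% | 30 | 18 | 12.0% | 15.0% | 32.0% |
| 10% | 30 | 12 | 8.0% | 10.0% | 28.0% |
| 20% | 15 | 27 | 18.0% | 20.0% | 28.0% |
| 20% | 30 | 24 | 16.0% | 20.0% | 36.0% |

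**If the denominator were treated patients only.** SAP 7.2.2.8 does not state one. Patients with Unknown use would drop out, but treated patients without a usable dose would still be No. Assume 45 treated patients. If 4 lack a dose and 20 are high dose, the coded share is 20/45 = 44.4%, against 20/41 = 48.8% among known doses. If 9 lack a dose and 18 are high dose, it is 18/45 = 40.0%, against 18/36 = 50.0%.

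**The case against.** **Section 6 may already settle the matter.** If the general rule governs, an absent dose stays missing and the catch-all applies only to evaluable doses. If the catch-all is a specified exception, nothing is contradicted. A reader might infer that the flag flatly contradicts section 6; because that section allows exceptions, the text supports only a tension. What stands is that the two readings give different tables from the same data. The specific wording of the catch-all and the two-level category list favour the literal reading.

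**The neighbouring row gives much of the answer.** A reader might infer that low dose, no steroid and no information cannot be separated at all. That goes too far. The parent row shows the no-steroid and Unknown-use counts, and parent Yes minus high-dose Yes gives the treated patients not flagged as high dose. What cannot be recovered is how many of that remainder had a documented low dose and how many had no usable dose.

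**The hidden group may be small or empty.** Drug and dose are named variables (protocol 9.3, Table 1), sites answer queries against source documents (9.6), and all eCRFs are open to remote review (9.8). This is fair: nothing in the documents suggests that steroid dose is often missing.

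**Excluding unknowns has its own bias.** If unrecorded doses were mostly low, coding them No would be nearly right, and a percentage among known doses would be too high. This also stands. It argues for showing the Unknown count rather than for relying on either percentage alone.

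**Conclusion.** The point holds as a small defect in a derivation rule. Followed as written, the rule counts patients without the needed information as not high dose, and the reported share can only be lowered or left unchanged. This rests on the literal reading of the catch-all and on documented Yes cases being correctly coded.

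The size is not knowable from the documents. It is zero if there are no unknowns. Under the assumptions above, 10% to 20% unknown turns a known-status share of 20.0% into 18.0% to 16.0%. These figures show scale and are not evidence of actual bias.

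A reader might also infer that the effectiveness results are affected. The visible text does not support that. The named subgroup (SAP 4.4) and the listed covariate (SAP 5.4) use any corticosteroid administration, and no visible PFS, OS, ORR or TTD analysis uses the high-dose flag. The study tests no hypothesis (SAP 3.1), so the effect is confined to a descriptive secondary table. The correction is worth making because it is nearly free.

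**What to change.** In the SAP section 5 derivation and the 7.2.2.8 category list, define the flag with three levels:

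- **Yes:** as now.
- **No:** only for documented non-use, or a documented dose below the SAP's existing cut-off.
- **Unknown:** when steroid use is Unknown, or when the drug or dose needed for conversion is missing or the drug has no listed ratio.

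State the percentage denominator in 7.2.2.8. A percentage among steroid-treated patients with a known dose, beside the percentage of all patients, is an optional addition. A short cross-reference to section 6 would remove the tension between the two rules.

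The cost is a line or two of SAP text and one extra category in one table. No new data collection is needed, and the cut-off does not change.

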#### 5.4 COVARIATES

- Age (2 categories)
- Body mass index (BMI) (3 categories)
- C-reactive protein (CRP) (3 categories)
- Estimated glomerular filtration rate (eGFR) (3 categories)
- Smoking history
- ECOG Performance Status
- ECOG Performance Status ①
- ECOG Performance Status ②
- Tumor histological type
- Presence or absence of sarcomatoid component
- Fuhrman grade (3 categories)
- Performance of nephrectomy
- Metastatic site: Lung

PFIZER CONFIDENTIAL

- Metastatic site: Liver
- Metastatic site: Bone
- Metastatic site: Brain
- Metastatic site: Regional lymph node
- Metastatic site: Distant lymph node
- Metastatic site: Other
- Number of metastatic organs (5 categories)
- Presence or absence of clinically important comorbidities
- Presence or absence of clinically important concomitant drugs
- Less than 1 year from diagnosis to the initiation of systemic therapy
- Karnofsky Performance Status <80%
- Hemoglobin value below the lower normal limit
- Corrected calcium value above the upper normal limit
- Neutrophil count above the upper normal limit
- Platelet count above the upper normal limit
- IMDC risk group
- Administration of corticosteroid therapy for irAEs

## 6 HANDLING OF MISSING VALUES

An absence of data for analysis will be treated as missing values, and no special imputation processing will be performed using statistical methods. In addition, the missing data regarding dates will be treated as follows:

- ✓ If "year" is unknown: Missing
- ✓ If "month" is unknown: July
- ✓ If "day" is unknown: day 15
- ✓ If "month" and "day" are unknown: July 1

Other than the above, the imputation of the missing values will not be performed, unless otherwise specified.

If the above imputation measures result in the reversal of dates when calculating the number of days (e.g., the number of days from the initiation to the end of the treatment), it will not be adopted for analysis.

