## **5 ENDPOINTS AND COVARIATES**

#### Handling of data on the number of days

The number of days from the start date to the target date will be calculated as follows:

- The target date is earlier than the start date = Target date — Start date
- The target date is on or after the start date = Target date — Start date + 1

The number of days will be handled as follows:

- ✓ 1 week = 7 days
- ✓ 1 month = 30.4375 days
- ✓ 1 year = 365.25 days

In addition, missing data will be imputed with reference to "6. HANDLING OF MISSING VALUES."

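### The SAP's reversed-date rule can drop only short intervals, so early events can be lost selectively and PFS, OS and TTD pushed slightly upward

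*SAP*

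**What the plan says.** SAP section 5 defines how days are counted and sends incomplete dates to section 6: "missing data will be imputed with reference to" that section. Section 6 sets three substitutions: the 15th for an unknown day, July for an unknown month, and 1 July when both are unknown. A date without a year stays missing.

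The last sentence of section 6 deals with conflicts. "If the above imputation measures result in the reversal of dates when calculating the number of days" (its example is the time from start to end of treatment), then "it will not be adopted for analysis". The section also states: "Other than the above, the imputation of the missing values will not be performed, unless otherwise specified".

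The SAP does not define *it*, which could be the imputed date, the interval or the patient. It does not say whether the patient leaves the Kaplan–Meier analysis or is censored, and it sets no lower bound at the start date. The visible text plans neither a count of affected patients nor a sensitivity analysis.

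PFS, OS and TTD are analysed in the efficacy analysis set (SAP 4.3: index date before 30 April 2022), with observation ending on 31 October 2022. Planned outputs are medians, 12-monthly rates for PFS and OS, and 3-monthly rates for TTD.

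**The concern.** Discarding a few unusable dates looks like neutral housekeeping, but whether a date is discarded depends on the outcome. An imputed end date can fall before treatment start only if the true end date came soon after it. A patient who progressed at 20 months and has a year-only progression date is kept. A patient who progressed at two months with the same defect may be dropped.

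On either natural reading of *it*, no usable time remains. If the interval is rejected, the record is gone. If only the imputed date is rejected, the date is missing and nothing may replace it. If the programmer instead censored the patient later, an early event would become event-free follow-up, an error in the same direction. At stake is a favourable tilt in the effectiveness results that no planned table is designed to show.

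**Working it through.** The documents state no figure on this point, so there is nothing to reproduce.

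**Inputs from the documents**
- Index dates in the efficacy set: 20 December 2019 to 29 April 2022, which is 12 + 366 + 365 + 119 = 862 days. The full window to 17 October 2022 is 12 + 366 + 365 + 290 = 1,033 days.
- Expected total of about 150 patients (Protocol 9.5). With uniform starts, 150 × 862/1,033 ≈ 125 are in the efficacy set.
- Median PFS of 13.8 months (Protocol section 7, combination arm of the phase 3 trial), used only for sizing.

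**Assumptions not in the documents:** uniform starts, exponential times, 10% yearly loss to follow-up unless stated, and the shares of partial dates.

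**Step 1: which intervals can be reversed (known start, partial end)**
- Day unknown: the start must fall on day 16–31 and the event later in the same month. The longest case is the 16th to the 31st, 15 elapsed days (16 with the SAP's +1).
- Day and month unknown: the start must be on or after 2 July and the event in the same year. The longest case is 2 July to 31 December, 182 elapsed days (183 counted). The exposed starts are 12 + 183 + 183 = 378 of 862 days, or 44%.
- Month only unknown: at most 153 counted days.
- Partial start, known end: at most 14 days (day unknown) or 182 days (day and month unknown).
- A date at the 31 October 2022 cut-off becomes 15 October, 1 July or 31 July 2022. All are later than 29 April 2022, so a patient in the efficacy set followed to the cut-off is never hit.

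**Step 2: size for PFS** (simulation of 1,000,000 patients). *Kept* means that the reversed event is retained midway between treatment start and the end of the known month or year.

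| Partial event dates | Events lost per 125 | 12-month PFS: true / SAP rule / kept (%) | Median: true / SAP rule / kept (months) |
|---|---|---|---|
| 20% day unknown | 0.17 | 54.74 / 54.80 / 54.73 | 13.80 / 13.83 / 13.80 |
| 2% year-only | 0.14 | 54.75 / 54.85 / 54.78 | 13.83 / 13.86 / 13.83 |
| 5% year-only | 0.36 | 54.77 / 55.02 / 54.86 | 13.83 / 13.93 / 13.86 |
| 10% year-only | 0.71 | 54.70 / 55.17 / 54.85 | 13.80 / 13.96 / 13.86 |
| 20% day unknown + 10% year-only | 0.89 | 54.65 / 55.23 / 54.83 | 13.77 / 14.00 / 13.83 |

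A separate run with 20% year-only dates gave about +1.0 point at 12 months and a median of 14.09 against 13.77 months. Keeping the events at the start date gave 13.86.

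**Step 3: check by hand.** Removing a fraction f of patients, all with events before 12 months, changes the 12-month rate from S to about S/(1 − f). For 10% year-only, f = 0.71/125 = 0.0057 and 54.70/0.9943 = 55.01, a rise of 0.31 points. The simulated gap between SAP rule and kept is 55.17 − 54.85 = 0.32. So about two thirds of the 0.47-point shift comes from dropping. The rest, 54.85 − 54.70 = 0.15, is error from imputation itself.

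**Step 4: compare with sampling error.** S(12) = 2^(−12/13.8) = 0.547. The half-width is 1.96 × √(0.547 × 0.453/125) ≈ 8.7 points.

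**Step 5: other cases**
- Partial dates on early censoring only (20% day unknown, 10% year-only, 40% yearly loss): 0.71 censored intervals lost per 125, and the 12-month rate moves from 54.74% to 54.78%.
- OS, assumed median 24–36 months: the 12-month rate rises by about 0.1–0.4 points.
- TTD, assumed median 8–12 months and ignoring the +13 days: the median rises by about 0.03–0.2 months.
- Avelumab TTD adds 13 days to the last dose. With only the day unknown, the end date becomes the 28th (15 + 13). Reversal then needs a start on day 29–31 and a last dose within 3 counted days.

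**The case against.** The strongest reply is that this hardly matters. The study is descriptive, charts are queried and remotely monitored (Protocol 9.6 and 9.8), and a year-only date within six months of starting a drug given every two weeks should be rare. A 10–20% share is probably high. Even then the shift is about a ninth of the confidence half-width or less. The loss is also partly visible, because summary statistics carry missing counts and the PFS section reports numbers of events and censorings. All of this stands. It limits the size, not the direction.

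Three stronger readings are tempting, and the documents support none of them.
- A reader might infer that the rule hits only events. Last visit, second-line start and nephrectomy dates fall under it too, and losing early censored intervals adds almost nothing.
- A reader might infer that PFS, OS and TTD *are* biased. That requires partial event dates to occur, and no rate is given.
- A reader might take the share of year-only events that would be reversed, just under 10%, as a study-level loss. It applies only to dates already reduced to the year. With 10% such dates, the loss is about 0.7 patients per 125.

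The reply is also right that a careless repair can do harm. Moving year-only reversals to the start date creates day-1 events. At 10% year-only this lowers 1-month PFS from about 95.15% to 94.85%, while the SAP rule raises it to 95.41%. The 12-month rate and the median are corrected either way. The first weeks of the curve cannot be recovered exactly by any placement.

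**Conclusion.** The point holds as a potential upward bias, probably small. The rule removes only short intervals, and where event dates are partial every scenario examined moved the PFS, OS and TTD estimates upward. For PFS, an assumed 2–20% share of year-only event dates gives about +0.1 to +1.0 points at 12 months and +0.03 to +0.3 months in the median. Part of that comes from the July substitution rather than the dropping. Day-unknown dates alone matter less. Combination and avelumab TTD are partly shielded by the +13 days.

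These sizes rest on uniform starts, exponential times and assumed partial-date shares. The undefined *it*, and the silence on what happens to the patient, need correcting whatever the share proves to be. The study's conclusions are unlikely to turn on this, but a bias of known direction that is so cheap to remove should be removed.

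**What to change.** Replace the last sentence of SAP section 6 with a rule along these lines:

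- If an imputed date precedes a known lower bound (the start date, or the last date on which the patient was known to be event-free), keep the patient and the event or censoring. Place the date inside the feasible window: at the bound or, preferably for year-only dates, midway between the bound and the end of the known month or year.
- Cap an imputed date only at a true upper bound for that endpoint: a recorded death date or 31 October 2022. Do not cap death or progression at second-line start. SAP 5.1 censors PFS there only when neither death nor progression is recorded, so a later recorded event still counts.
- Report, for each endpoint, the number of patients whose date was adjusted. A sensitivity analysis that omits them would be a useful addition.

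The day count in section 5 already copes with this, since a date at the bound gives 1 day. The cost is about a sentence of SAP text and a few lines of code. The downside is that these few times are approximate.
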